## 15.22.9 Overdose

Overdose is defined as any dose higher than the protocol prescribed dose of study drug. Occurrences of overdose leading to an AE will be reported on the AE eCRF. An overdose leading to an SAE will be reported to the Sponsor according to the procedure described in Section 15.22.5.

## 15.22.10 Follow-up of Adverse Events

Patients with an ongoing SAE will be followed until the event is resolved, the significant changes return to baseline, the condition stabilizes, the event is no longer considered clinically significant by the Investigator, the patient withdraws consent, or the patient is lost to follow-up. This may imply that follow-up will continue after the patient has left the study and that additional investigation may be requested by the Sponsor. If the severity or relationship to study drug worsens for an ongoing SAE, a follow-up SAE report should be sent to the Sponsor within 24 hours after the Investigator becomes aware of the change in status.

All non-serious adverse events will be followed through the study exit visit. If a non-serious AE is first identified at the last scheduled study contact, the event will be recorded on the AE eCRF with the current status noted, but no further follow-up is required.

#### 15.22.11 Follow-up of Post-study Serious Adverse Events

Should the Investigator become aware of a new SAE that occurs within 30 days after the last scheduled study contact and the event is determined by the Investigator to be related to the study drug, the SAE should be reported to the Sponsor and followed in accordance with the procedures described in this protocol.

# **16 STUDY ENDPOINTS**

#### **16.1 Primary Endpoints**

Safety as measured by:

- Occurrence of ocular and systemic serious adverse events and adverse events
- Changes in standard clinical laboratory tests (serum chemistry, hematology, coagulation) and ADA levels
- Changes in vital signs and physical and ophthalmic examinations

#### **16.2** Secondary Endpoints

Pharmacokinetics and Pharmacodynamic Markers

- Plasma levels of ICON-1 following intravitreal injections of ICON-1
- Change in circulating TF and serum cytokine levels following intravitreal injections of ICON-1
- Characterization of immunophenotyping patterns

Pharmacodynamic and Biological Activity

• Change in tumor size (thickness, volume) as assessed by imaging techniques (CFP, FA, sdOCT, ultrasound, ICG angiography, EDI-OCT) from baseline

## **16.3** Exploratory Endpoints

- Characterization of the genetic profile of the tumor (Type 1 or Type 2), and associated changes in the tumor with ICON-1 treatment
- Characterization of pathologic findings of the tumor (ICON-1 target engagement within the tumor, TF and PAR2 expression, characterization of immune infiltrate, and alterations of the vasculature)
- ICON-1 and proteomic analysis (TF and other cytokine levels) of the vitreous humor

# **17 STATISTICAL ANALYSIS AND METHODS PLANNED**

#### 17.1 Statistical Analysis Plans

This phase 1 study is exploratory and its sample size is not determined by statistical power considerations. Hence, no inferential testing will be performed. Data analysis for this study will be geared toward descriptive and graphical summaries.

As descriptors of the three cohorts, univariate data summaries will be provided. For continuous endpoints, summary statistics will include number of patients, mean, median, standard deviation, minimum, and maximum. For categorical endpoints, summary statistics will include number of patients, frequency, and percentages.

All patients who receive ICON-1 will be considered evaluable and will be included in the analysis. Exploratory analyses of the data not described in the following subsections may be conducted as deemed appropriate. The baseline evaluation will be defined as the last evaluation prior to the first study treatment. More details will be provided in the Statistical Analysis Plan (SAP).

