## **10.3** Discussion of Study Design

In this Phase 1 study ICON-1 will be intravitreally administered for the first time in patients with uveal melanoma. The starting dose of ICON-1 ( $300 \mu g/100 \mu l$ ) is the maximum dose administered in the Phase 1 single IVT administration study, and the ongoing Phase 2 repeated IVT administration study in patients with CNV secondary to AMD. As this dose has been administered to approximately sixty (60) patients and found to be well tolerated to date, a cohort of two patients which may be expanded to three patients is thought to be sufficient to make a determination to escalate to the subsequent higher dose level of two doses of 0.3 mg ( $300 \mu g/100 \mu l$ ) ICON-1 administered one week apart. The cohort size is increased (cohort 2; n=3, cohort 3; n=5), as the dose and volume is escalated in subsequent cohorts. Each of these cohorts may be expanded by one patient in the event of a DLT. A toxicity rate of one third or less in a cohort is within the accepted clinically observed toxicity standards to establish a preliminary safety profile of ICON-1 administered in patients with uveal melanoma and to support additional studies. In this study, the maximum administered dose will not exceed 0.6 mg ( $300 \mu g/100 \mu l + 300 \mu g/100 \mu l$ ) ICON-1.

Pharmacodynamic and biologic activity markers are utilized to explore preliminary evidence of activity with respect to target engagement (ICON-1 binding to TF in the tumor) as measured by tissue staining of the tumor and supporting stroma within the enucleated eye, assessment of immune infiltrate in the tumor, measurement of TF and PAR2 dependent cytokines/chemokines in blood, TF and cytokine levels in vitreous humor, and changes in tumor size and volume as well as changes in BCVA by ETDRS. Ophthalmic ultrasound is utilized to assess and measure changes in the size of the ocular tumor. Ophthalmic imaging including sdOCT, EDI-OCT, FA, ICGA, and CFP are utilized for measuring and evaluating changes in vasculature, in the anatomic layers of the retina, choroid, and ocular tumor and the associated pathology of the lesions (such as exudation).

The study duration, including a one to two week dosing period prior to a scheduled enucleation or plaque placement procedure is considered an adequate period to assess safety, PK and preliminary pharmacodynamic and biologic activity without delaying or interfering with standard of care treatment for uveal melanoma.

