#### 14.2 Visit 2 (All cohorts): Baseline (Treatment Day 0)

Baseline assessments will be completed on Day 0. The following procedures will be performed:

- Vital signs
- Perform the following ophthalmic procedures:
  - Best-corrected visual acuity by ETDRS (both eyes)
  - Slit lamp biomicroscopy (both eyes)
  - IOP; cohorts 1 and 2: pre-injection (both eyes) and post injection (study eye only), cohort 3: pre-injection (both eyes) and post each injection (study eye only)
  - Dilated ophthalmoscopy (study eye only)
- Blood sample (pre-injection and 4 hours ±1 hour after dose administration. For cohort 3, after the second injection) for pharmacodynamic assessment
- Blood samples (pre-injection and 4 hours ±1 hour after dose administration. For cohort 3, after the second injection) for pharmacokinetic assessment
- Administration of intravitreal injection(s)
- Assessment of adverse events
- Record concomitant medications

• Instruct patients to contact site study personnel immediately if their treated eye becomes red, sensitive to light, painful, or develops a change in vision.

#### 14.3 Visit 3 (All cohorts): Day 1

The following procedures will be performed at Day 1:

- Vital signs
- Perform the following ophthalmic procedures:
  - Best-corrected visual acuity by ETDRS (study eye only)
  - Slit lamp biomicroscopy (study eye only)
  - IOP (study eye only)
- Blood sample for pharmacodynamic assessment
- Blood sample for pharmacokinetic assessment
- Assessment of adverse events
- Record concomitant medication

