#### 17.6 Safety Analyses

Safety will be assessed through summaries of adverse events, changes in laboratory test results (serum chemistry, hematology, coagulation), and changes in vital signs and physical and ophthalmic examinations. Adverse events will be mapped using MedDRA. Systemic levels of

anti-drug antibodies (ADA) during the study will be collected for each patient. If there are sufficient numbers of patients exhibiting systemic levels of ADA, summary statistics by cohort will also be provided.

All collected adverse event data will be listed by cohort, study site, and patient number. All Adverse Events of Special Interest (AESIs) occurring on or after intravitreal injection will be listed and summarized by cohort. All adverse events occurring on or after treatment on Day 0 (treatment emergent adverse events, TEAEs) will be summarized by cohort. In addition, all serious adverse events, including deaths (if any), will be listed separately. Finally, all ocular adverse events will be listed and tabulated with events for the study and fellow eye summarized separately.

Changes in laboratory data will be summarized by cohort.

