## 17.8 Pharmacokinetic and Pharmacodynamic Markers Analyses

Pharmacokinetic analyses will be conducted on data from patients who have received at least 1 dose of ICON-1 and have at least one post-dose sample collected to allow estimation of the PK parameters.

Individual (patient) plasma ICON-1 concentrations at each sampling time will be listed; corresponding summary statistics at each sampling time will be calculated for the ICON-1. Plasma ICON-1 versus time profiles (with concentrations on both a log and linear scale) will be plotted for each patient; corresponding summary time plots will likewise be constructed for cohort.

When applicable, pharmacokinetic parameters will be calculated using non-compartmental techniques from plasma ICON-1 concentrations and will include the following parameters:  $t_{1/2}$ ,  $C_{max}$ ,  $T_{max}$ , and AUC0- $\infty$ . Individual ICON-1 PK parameters will be listed for each patient, and summary statistics will be calculated for each cohort.

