## **17.10** Sample Size Determination

Up to 13 patients with uveal melanoma involving the posterior uveal tract will be enrolled from approximately seven to ten centers in the United States. Patients who discontinue before the one week safety evaluation following their last injection may be replaced. This study is exploratory and its sample size is not determined by statistical power considerations and no sample size calculations were performed.

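### Adverse-event and PK-parameter summaries are by cohort, so tabulated single-dose safety rests on 2 patients although 5 share the same first 0.3 mg dose, and first- and second-dose events are mixed

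*Combined protocol and SAP*

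**What the plan says.** The primary objective (Section 9.1) covers both single and repeated injections. Section 10.1 doses every cohort on Day 0 and only cohorts 2 and 3 again on Day 7. The Day 0 dose is 0.3 mg in cohorts 1 and 2 and 0.6 mg in cohort 3. The first post-dose visit is common to all: "Visit 3 (All cohorts): Day 1" (Section 14.3).

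The summary unit is the cohort:
- Section 17.1, in general: "As descriptors of the three cohorts, univariate data summaries will be provided".
- Section 17.6, on adverse events: "All adverse events occurring on or after treatment on Day 0 (treatment emergent adverse events, TEAEs) will be summarized by cohort". Events of special interest and laboratory changes are also by cohort.
- Section 17.8, on PK parameters: "Individual ICON-1 PK parameters will be listed for each patient, and summary statistics will be calculated for each cohort". It does not say which dose the parameters describe in patients who are sampled after both.

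Two outputs are finer. Section 17.7 summarises biological activity over time for each patient. Section 17.8 lists plasma concentrations by patient and summarises them at each sampling time.

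The study is descriptive: "Hence, no inferential testing will be performed" (Section 17.1). That section also leaves room for further exploratory analyses and defers detail to an SAP.

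**The concern.** Until the second injection, a cohort 2 patient has had the same treatment as a cohort 1 patient. Tabulating the two apart leaves 2 patients in the only adverse-event column that is purely single-dose, while 3 more with the same first dose sit in a column that also contains events after dose 2. The cohort 3 column has the same mixture.

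Dose number matters here on the protocol's own evidence. Section 8.2 reports that repeat intravitreal dosing in mini-pigs caused ocular inflammation that was clearest following the second dose, and puts this down to a probable species-specific response. Ocular inflammation is both an event of special interest and a component of the dose-limiting toxicity definition. Splitting human events by dose is the direct way to see whether the animal pattern recurs, and the planned tables do not do it. Section 12.3 gives 0.3 mg as the highest dose tested before, so tolerability of a first 0.6 mg dose is also new information.

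**Working it through.** **Inputs**
- Cohort 1: "a cohort of two patients which may be expanded to three patients" (Section 10.3).
- Cohorts 2 and 3: "cohort 2; n=3, cohort 3; n=5" (Section 10.3).
- Maxima: 3, 4 and 6 (Section 12.4).
- Power, effect size, SD: none. Section 17.10 says "its sample size is not determined by statistical power considerations and no sample size calculations were performed".

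**The plan's own figure.** The cohort maxima give 3 + 4 + 6 = 13, which reproduces the stated limit of 13 patients. Without expansion the total is 2 + 3 + 5 = 10.

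**Group sizes before dose 2**
- First dose 0.3 mg, cohorts 1 and 2: 2 + 3 = 5 (maximum 3 + 4 = 7).
- Cohort 1 alone: 2 (maximum 3).
- First dose 0.6 mg, cohort 3: 5 (maximum 6).

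**Zero-event bound.** If none of n patients has an event, the one-sided 95% upper bound on the rate is 1 − 0.05^(1/n):
- n=2: 1 − 0.05^(1/2) = 0.776
- n=3: 1 − 0.05^(1/3) = 0.632
- n=5: 1 − 0.05^(1/5) = 0.451
- n=7: 1 − 0.05^(1/7) = 0.348

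A cohort expands only after a dose-limiting toxicity. The bounds at n=3 (as cohort 1's maximum) and n=7 are therefore for another event type, or for a window that the toxicity falls outside.

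**Chance of seeing at least one event**, 1 − (1 − p)^n. The documents give no expected rate. Section 10.3 only calls one third or less acceptable, so the rates p are assumptions.

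| True rate | n=2 | n=5 |
|---|---|---|
| 10% | 19% | 41% |
| 20% | 36% | 67% |
| 33% | 56% | 87% |

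**How far pooling is like-for-like**
- Through Day 1: Sections 14.1 to 14.3 give cohorts 1 and 2 the same procedures. Cohort 3 differs at Visit 2. It has two injections, IOP after each, and post-dose blood samples timed from the second.
- After Day 1: cohort 1 has no Day 7 visit. Its surgery is scheduled independently of the study, at least 4 days after the injection (Section 14.6), with Visit 6 on that day or the day before. Visit 6 can fall as early as Day 4 − 1 = 3, and no upper limit is stated. Cohort 2 reaches dose 2 on Day 7 ± 2, that is Day 5 to Day 9. Adverse-event follow-up before dose 2 is therefore unequal.
- Laboratory tests: none on Day 0 (unless screening is done that day, before injection) or Day 1. The first scheduled post-dose sample is Visit 6 in cohort 1 and Day 7 in cohort 2, and Section 14.4 does not say that the Day 7 sample precedes the injection. There is no common post-dose sample to pool.
- Adverse events: Section 15.22 records onset dates and lists no onset times. Section 12.5 records the date and time of treatment. An event starting on the Day 7 dosing date cannot be placed before or after dose 2 from these fields alone.

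**What already shows data before dose 2.** Section 15.19 schedules PK samples for cohorts 2 and 3 on Day 0 after injection, on Day 1, and on Day 7 before injection. All precede dose 2, and Section 17.8 lists and summarises them by sampling time. Day 7 ophthalmic procedures come before dosing (Section 14.4) and feed the per-patient summaries in Section 17.7.

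**The case against.** The strongest reply is that nothing turns on these tables. No hypothesis is tested and no intervals are planned, so no error rate changes. Escalation uses dose-limiting toxicity counts within each cohort (Section 12.4). With 10 to 13 patients the individual listings carry most of the information, and Section 17.6 lists every adverse event by cohort, site and patient. Section 17.1 permits extra analyses and defers detail. All of this stands, and it makes the point one of presentation and precision. The deferral allows the missing summaries but does not commit to them, and the unit that is stated is the cohort.

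The second reply is that pooling is clean only through Day 1. That stands too, and it limits the remedy.

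A reader might infer more than the documents support:
- That everything is reported by cohort only. It is not: activity is summarised per patient over time and plasma levels by sampling time.
- That a single 0.6 mg dose is never shown. Cohort 3 plasma values and ophthalmic findings before dose 2 do appear. The statement fits only adverse events and other outputs not split by dose.
- That a first-dose comparison of 0.3 mg with 0.6 mg is lost. None is planned and it is not an objective, so its precision is no measure of the gap.
- That pooling gives n=5 throughout. Pre-procedure and end-of-study single-dose results rest on cohort 1 whatever is done.

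**Conclusion.** The point holds within limits. For adverse events and events of special interest, tabulated single-dose safety rests on 2 patients (at most 3) when 5 (at most 7) share the same first dose and the same visits through Day 1. The cohort 2 and 3 columns do not separate events after dose 1 from events after dose 2, and the PK parameters carry no dose number. If no events occur, the difference is an upper bound of 78% against 45%.

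These bounds are the review's yardstick; the plan does not propose them. They assume the planned cohort sizes and a common event rate in cohorts 1 and 2. They compare like with like through Day 1; beyond that, follow-up is unequal and must be shown. This is a worthwhile, cheap improvement to how the primary objective is presented. It does not undermine the escalation rule or any inference.

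**What to change.** Keep the by-cohort tables and specify the following in Sections 17.1, 17.6 and 17.8 or in the SAP:

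1. **First-dose summaries of Day 0 and Day 1 measures** (PK, PD, IOP, BCVA, vital signs): 0.3 mg pooled over cohorts 1 and 2, and 0.6 mg from cohort 3.
2. **TEAE and AESI tables by onset before or after dose 2.** Pool the first-dose 0.3 mg column over cohorts 1 and 2. End the first-dose window before the earliest of the Day 7 injection, Visit 6 or surgery, and no later than Day 9. Show follow-up days for each column. State a rule for events whose onset date is the Day 7 dosing date.
3. **PK parameters labelled by dose number.**

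Do not pool laboratory changes; leave them by cohort.

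The cost is analysis-plan wording and a few extra tables, built from onset dates and dosing records that are already collected. No visit or procedure is added. The drawback is that follow-up in the pooled adverse-event column is unequal after Day 1, which is why the follow-up days must be shown.

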#### 17.2 Analysis of the Conduct of the Study

The number of patients enrolled will be tabulated by study site and cohort. Patient disposition (the number of subjects enrolled, treated, and completing the study) will be tabulated by cohort. Subject discontinuations and reasons for discontinuation will be summarized.

#### 17.3 Handling of Dropouts or Missing Data

Patients who discontinue from the study prior to completing the one week safety evaluation following their last injection may be replaced.

## 17.4 Analysis of Treatment Arm Comparability

Summary statistics of patient demographics, such as age, sex, and race will be provided by cohort to assess comparability. Other baseline characteristics such as genetic profile of the tumor may be summarized.

#### **17.5** Treatment Exposure

The total dose received will be summarized by cohort. The dose level, and number of doses received will also be summarized by cohort. Study drug administration data will be listed for each patient.

#### 17.6 Safety Analyses

Safety will be assessed through summaries of adverse events, changes in laboratory test results (serum chemistry, hematology, coagulation), and changes in vital signs and physical and ophthalmic examinations. Adverse events will be mapped using MedDRA. Systemic levels of

anti-drug antibodies (ADA) during the study will be collected for each patient. If there are sufficient numbers of patients exhibiting systemic levels of ADA, summary statistics by cohort will also be provided.

All collected adverse event data will be listed by cohort, study site, and patient number. All Adverse Events of Special Interest (AESIs) occurring on or after intravitreal injection will be listed and summarized by cohort. All adverse events occurring on or after treatment on Day 0 (treatment emergent adverse events, TEAEs) will be summarized by cohort. In addition, all serious adverse events, including deaths (if any), will be listed separately. Finally, all ocular adverse events will be listed and tabulated with events for the study and fellow eye summarized separately.

Changes in laboratory data will be summarized by cohort.

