## 14.1 Visit 1 (All cohorts): Screening (Day -7 through 0)

Screening must take place within 7 days prior to the intravitreal injection on Day 0 (Baseline Visit). Patients will undergo Screening assessments to determine if they are eligible to enroll in the study. If there is study drug available at the clinical site, Screening assessments to confirm eligibility may be performed on Day 0, prior to any intravitreal injection and any additional baseline specific assessments.

The following procedures will be performed at Screening:

- Obtain written informed consent
- Obtain demographic data
- Obtain medical and ocular history including surgical and medication history. Prior and concomitant medications taken within the last 30 days will be recorded.
- Vital signs
- Blood samples for clinical laboratory tests (serum chemistry, hematology and coagulation), prior to injection of Fluorescein and ICG dye (as applicable)
- Blood sample for anti-drug antibody levels, prior to injection of Fluorescein and ICG dye (as applicable)
- Blood sample for serum pregnancy test (women of child bearing potential only), prior to injection of Fluorescein and ICG dye (as applicable)
- Abbreviated physical examination including height and weight
- Perform the following ophthalmic procedures:
  - Best-corrected visual acuity by ETDRS-like charts (both eyes)

- Slit lamp biomicroscopy (both eyes)
- IOP (both eyes)
- Dilated ophthalmoscopy (both eyes)
- Color fundus photography (both eyes)
- sdOCT (study eye only)
- EDI-OCT optional according to investigator judgment (study eye only)
- Ophthalmic ultrasound (study eye only)
- Fluorescein angiography (both eyes)
- ICG angiography optional according to investigator judgment (both eyes)

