## 15.22 Evaluation of Adverse Events

Adverse events (AEs) will be monitored continuously during the study from the time that the subject has provided written informed consent through the subject's last day of study participation. AEs may be reported spontaneously by the subject, discovered by Investigator or study staff through questioning, or observed through physical examination or other means. It is the responsibility of the Investigator to assess and document all AEs that occur during the course of the study, regardless of the causal relationship with the study drug.

The following information will be collected for all AEs and recorded on the subject's source document and AE eCRF:

- Event description (diagnosis preferred, if unknown, record the signs/symptoms)
- Onset and resolution dates
- Severity (intensity)
- Frequency (intermittency)
- Relationship to study drug (causality) as determined by the Investigator
- Seriousness
- Action taken with study drug
- Corrective action taken
- Outcome

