### 21.1 Appendix A: Study Flowchart and Assessments – Cohort 1 (Patients Undergoing Enucleation or Brachytherapy)

## Iconic Therapeutics Inc. IT-003

Study Day	Screening  Day -7 to 0	Baseline Treatment Day 0	Day 1	NA for Cohort 1	Procedure Assessments (On or 1 day prior to Surgical Procedure  day)	End of Study 30 days ±5 days post Surgical Procedure	Early Termin- ation
Visit	1	2	3	$4^2 \& 5^2$	6	7	ЕТ
Enhanced Depth Imaging Optical Coherence Tomography (optional according to investigator judgment)	SE				SE		SE 
Ophthalmic Ultrasound	SE				SE	SE 	SE 
Fluorescein Angiography	OU				OU		OU 
ICG Angiography (optional according to investigator judgment)	OU				OU		$OU^{10}$
Pharmacodynamic Assessments (blood sample pre and post treatment)		X 	Х		X		X 
Pharmacokinetic Assessment (blood sample pre and post treatment)		X 	X				X 
Intravitreal Injection: COHORT 1		X					
Scheduled Enucleation or Plaque Placement Procedure  (≥4 days after injection according to standard of care)					Х		
Mandatory Vitreous and Tumor Sample for Enucleation Patients 					Х		
Adverse Events		Х	Х		Х	Х	Х
Concomitant Medications	Х	Х	Х		Х	Х	Х

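### The study-eye/fellow-eye table in section 17.6 has no onset limit, so eye events that began before any ICON-1 can be counted in it

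*Combined protocol and SAP*

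**What the plan says.** Collection is set in section 15.22: "Adverse events (AEs) will be monitored continuously during the study from the time that the subject has provided written informed consent". Section 15.22.6 adds that patients are to be asked about problems since their last visit at every scheduled or unscheduled visit. It also provides for reporting certain serious events that fall between consent and dosing.

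Section 17.6 then sets out the outputs:

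- AESIs are listed and summarized by cohort only if they occur on or after injection.
- The general summary is limited in the same way: "All adverse events occurring on or after treatment on Day 0 (treatment emergent adverse events, TEAEs) will be summarized by cohort".
- The by-eye output carries no time limit: "Finally, all ocular adverse events will be listed and tabulated with events for the study and fellow eye summarized separately".

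Section 17.1 restricts the analysis to patients who received ICON-1. That selects patients, not events.

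On scheduling, the Screening list in section 14.1 contains no adverse event item. The item "Assessment of adverse events" first appears at Visit 2 (section 14.2). In Appendices A and B the "Adverse Events" row is blank under Screening and first marked at Day 0.

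**The concern.** Ocular adverse events are part of the primary endpoint (section 16.1). The study has no control group, so the by-eye table is the only planned contrast between a treated and an untreated eye. A reader will take its study-eye column to describe what followed ICON-1.

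Screening involves several procedures before any drug is given: contact tonometry, dilation and fluorescein angiography in both eyes, and ultrasound and OCT in the study eye only. If one of these causes an eye event, the table as worded counts it. The general summary, which is limited to events on or after treatment, leaves it out. Two tables built from the same data would then disagree without explanation, and in cohorts this small a single event moves a percentage visibly.

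**Working it through.** **The plan's own figure.** The only sample-size figure is the maximum of 13 patients. It reproduces from the cohort maxima in section 12.4: 3 + 4 + 6 = 13. The planned sizes sum to 2 + 3 + 5 = 10. No power calculation exists to check, and the point does not depend on one.

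**Does a pre-dose event reach the table?**

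1. It can enter the database: section 15.22 starts at consent, and the Day 0 question in section 15.22.6 reaches back to the previous visit.
2. The patient is analysed if later dosed (section 17.1).
3. The AESI and general summaries exclude the event; the by-eye sentence does not.
4. Nothing else in the supplied text adds a limit.

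So the event can be tabulated by eye and be absent from the treatment-emergent summary.

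**Size for one patient.** The by-eye sentence does not name cohorts. I assume it follows the by-cohort convention of section 17.1. If a patient's only study-eye event was pre-dose, the rise is 100/n percentage points:

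| | Cohort 1 | Cohort 2 | Cohort 3 |
|---|---|---|---|
| Planned n | 2 | 3 | 5 |
| Rise (points) | 50 | 33.3 | 20 |
| Maximum n | 3 | 4 | 6 |
| Rise (points) | 33.3 | 25 | 16.7 |

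**How often.** The documents give no rate. Let p be an assumed chance that a patient has a pre-dose study-eye event. The chance of at least one such patient is 1 − (1 − p)^n:

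| Assumed p | n = 10 | n = 13 |
|---|---|---|
| 2% | 18% | 23% |
| 5% | 40% | 49% |
| 10% | 65% | 75% |

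These chances are upper bounds on a visible change, because they also count patients who have a post-dose study-eye event and so appear in the table anyway.

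**Same-day events.** Screening may be done on Day 0. Section 15.22 lists onset dates for events, while section 12.5 records the date and time of dosing. Dates alone cannot order a Day 0 event against the injection.

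**Which treatment-emergent window.** Section 15.22.1 ends the window 30 days after the last dose; section 17.6 gives no end. Surgery is at least 4 days after the last injection (section 14.6), and Visit 7 is 30 ± 5 days after surgery (section 14.7). Visit 7 therefore falls at least 4 + 25 = 29 days after the last dose at the earliest, and at least 4 + 30 = 34 days nominally. A fix that borrowed the 30-day window could drop post-dose eye events first seen at Visit 7, where brachytherapy patients have a full eye examination.

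**The case against.** The strongest reply is that little hangs on this table. All adverse events are listed by cohort, site and patient with onset dates, so among 10 to 13 patients a pre-dose event can usually be spotted. The treatment-emergent summary is correctly limited and includes ocular events. No inferential testing is planned. Escalation rests on the Safety Review Committee's assessment of dose-limiting toxicities (section 12.4), not on this tabulation. Section 17.1 also leaves detail to a SAP, and the restriction may be specified there; the supplied text contains no such provision. All of this stands, and it keeps the point minor. It does not make the sentence in section 17.6 right.

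A second reply is that one part of the adverse event definition in section 15.22.1 refers to occurrences during or after study treatment. Another part has no time limit, and section 15.22 is explicit about consent, so this does not settle the matter.

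A reader might infer something stronger: that the plan holds conflicting start rules, and that sites following the flowchart would fail to record pre-dose events. The documents do not support that. No passage says collection begins at Day 0. A blank Screening cell schedules no assessment, but it does not cancel section 15.22, and the question asked at Day 0 covers the time since Screening. What remains is a scheduling mismatch.

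A reader might also take the 20 to 50 point shifts as the expected bias. They apply only to a patient with no post-dose study-eye event. Such events may be common: the earlier single-dose study of 18 patients reported conjunctival hemorrhage (n=5), and floaters and conjunctival edema (n=3 each).

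**Conclusion.** The point holds as a defect in one descriptive table. As written, eye events from before any ICON-1 can be counted in the by-eye tabulation, which then need not agree with the treatment-emergent summary. The effect is 50, 33 or 20 points in a cohort for one patient whose only study-eye event was pre-dose, assuming planned cohort sizes and tabulation by cohort. The frequency is unknown, and the 2% to 10% range above is assumed. No escalation decision or formal test changes. The missing Screening entry is a secondary matter of scheduling and does not show that data would be lost.

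**What to change.** - **Section 17.6.** Replace the by-eye sentence with wording to this effect: *every ocular adverse event is listed; those with onset on or after the first ICON-1 injection through the end of study are tabulated by cohort, study eye and fellow eye separately; pre-dose events appear in the listing only.*
- **Day 0 events.** Record whether onset was before or after injection.
- **Treatment-emergent window.** Use one definition in sections 15.22.1 and 17.6, chosen so that post-dose events found at Visit 7 are kept.
- **Scheduling.** Add an adverse event assessment after consent to section 14.1 and to the Screening column of Appendices A and B, in line with sections 15.22 and 15.22.6.

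The cost is one sentence in section 17.6, one aligned definition, one line in section 14.1, two flowchart marks and one data item. Patient management does not change.
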